5.1. Inclusion criteria for veterans

- Adult, aged: ≥ 18
- Male or female individual with a stoma
- Stoma debut for ≥ 3 months
- Individual who require a re-evaluation of ostomy product(s) in a stoma care clinic due to issues with leakage
- Must have provided a written informed consent for participation in the study prior to any specific procedures

5.2. Inclusion criteria for NPD subgroup

- Adult, aged: ≥ 18
- Male or female individual with a stoma
- Stoma debut for < 3 months
- Must have provided a written informed consent for participation in the study prior to any specific procedures

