An article has been published in *British Journal of Nursing* (2) about the consensus guidelines to encourage nurses to choose ostomy products based on assessment of the individual body profile of the user. The paper shows how the consensus guidelines were developed and presents concept and purpose of the 6 steps in the Body Assessment Tool in hope of providing nurses a more structured and "right from the start" approach when choosing ostomy products. However, the Body Assessment Tool needs to be evaluated in clinical settings to document the usability among nurses and to explore its impact on selection of ostomy product(s) together with a potential improvement of leakage incidences and the user's leakage-related quality of life using the validated OLI score (Ostomy Leakage Impact Tool)(3).

Furthermore, it is of interest to explore usability of The Body Assessment Tool in the group of newly stoma patients (i.e. newly patient discharged (NPD)) as they may have a potentially larger extent of change of their peristomal body profile post-surgery compared to experienced people with a stoma (i.e. veterans). A subgroup of NPDs will therefore be recruited at one clinical site,
Meilahden tornisairaala, Finland

2. Hypothesis

The hypothesis is that with the Body Assessment Tool in combination with the use of the current guidelines and practices, nurses will be able in a standardised way to choose the most appropriate ostomy product(s) for the given user and may thereby help improving the QoL of the user by reducing the users concerns about leakage and preventing the incidences of leakage.

3. Objectives

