3.2. The secondary objectives

- To explore if the use of Body Assessment Tool and related change of ostomy product(s) have an impact on the leakage associated QoL (based on the OLI score)- see appendix C. The OLI score includes three domain scores:
 - emotional impact
 - usual and social activities
 - coping and in control
- To evaluate the incidences of leakage before and after change of ostomy product(s) (the question will be included in a leakage questionnaire in addition to the OLI score – see appendix D).

4. Study design

The study is a 1-sequential, 1-arm, non-randomised, non-blinded, multi-center (between 20 to 40 sites in total) non-interventional 4-5-week clinical investigation in which the Body Assessment Tool will be evaluated for its usability by ostomy nurses using the Nurse Evaluation Form and to explore if the change of ostomy product(s) can reduce the user's concerns about leakage and have a positive impact on QoL related to leakage (estimated by the OLI score). For evaluation of the number of leakage incidences the last 7 days pre- and post-change of ostomy products a questionnaire is prepared including a definition of leakage and images for support.

Blinding is not applicable as change of ostomy product(s) cannot be blinded for either the user or nurse. Randomization is not applicable as there will be no comparison to a specific ostomy product or control group. The subjects will change their ostomy product(s) based on their individual body profile assessment and the selection of ostomy products will vary in between subjects and will not be dictated by this protocol.

The NPD subgroup will follow the same protocol as the veterans. However, the data (NPDs vs. veterans) will not be compared due the potentially difference in the change of peristomal body profile. The NPD data will be regarded and handled as exploratory.

All assessments will be based on questionnaires either completed by the nurse or user. Usability data will only be analyzed using descriptive methods. Whereas the OLI score results will be analyzed by descriptive methods (sub-questions in OLI score) and paired t-test (domain scores). The number of leakage episodes will be analyzed by paired t-test.

The study will include 1 visit at the clinic and at least 1 phone call visit to the user (end-of study phone visit). The number of phone calls will vary depending on the user's need for support.

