Prior to screening the nurse identifies potential patients who require a re-evaluation of their current ostomy products due to ongoing product issues (please refer to section 5 '*In- and exclusion criteria*'). If the patient is interested in study participation the subject must sign an informed consent after having received verbally and written information about the study. When signed the subject can undergo the screening assessment and if found eligible the subject can be enrolled in the study.

Following enrollment, the nurse will perform body profile assessment (the stoma and peristomal area) of the subject using the Body Assessment Tool. Based on the result the nurse will select the most appropriate ostomy product(s) for the subject. The body assessment tool that has been filled out for each participant will be stored in the study participant file. At the visit the subject will also be asked to evaluate the impact of leakage and fear of leakage on their QoL using the OLI-score together with recalling the number of leakage incidences the last 7 days. This questionnaire will also be stored in the study participation file. The participant

will leave the clinic with new ostomy products and be instructed to use them for the next 4-5 weeks. The participant will also receive a second questionnaire to be filled in at home after 4-5 weeks.

After 4-5 weeks, the nurse will contact the subject by phone or in a new scheduled visit to the clinic to remind the participant, if needed, to evaluate the impact of leakage on QoL/fear of leakage using the OLI score together with recalling the number of leakage incidences in the last 7 days. The subjects will send the questionnaires with a patient code directly to Coloplast. Patients will be encouraged to send in the second questionnaire even if they have discontinued using the recommended ostomy products also to know the reason for discontinuation.

After all subjects at a given study site have been included, the nurse will evaluate the Body Assessment Tool based on his/her experience of the tool in the clinic, using the Nurse Evaluation Form.

Anonymous data – including the questionnaire and the body assessment tool for each participant and the Nurse Evaluation Form will be sent to Coloplast for analysis.

5. Inclusion- and exclusion criteria

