5	
De Internationella Consensus Guidelines rekommenderar att man, utöver att välja produkt baserat på Kroppsprofil, även tar patientens peristomala hud och övergripande situation i beaktning. Genom att överföra det antal gånger de fyra faktoreerna har påverkat valet av produkt från det ifyllda verktyget Kroppsprofil, kan vi bestämma, vilka faktorer utöver Kroppsprofil, som har varit viktigast i valet av produkt.
 
Överför från verktyget Kroppsprofil det antal gånger de fyra faktoreerna har haft påverkan på produktval
			
	Den peristomala huden	Patientens allmänna tillstånd	Patientens tillgång till hjälp i hemmet	Patientens förmågor

Andra förhållanden du har tagit i beaktning:
 <hr/> <hr/>				
6	
Beskriv med egna ord hur du upplever att verktyget Kroppsprofil, som baserar sig på de Internationella Consensus Guidelines, har fungerat i klinisk praxis?
 <hr/> <hr/> <hr/>			
7	
Vill du rekommendera verktyget Kroppsprofil till andra stomiterapeuter/vårdpersonal?
 
Markera med X
			
	JA	NEJ	Varför?	
			<hr/> <hr/>	

Tusen tack för hjälpen!

14. Appendix C – The OLI Score

The below tables show the scoring weights for each item from the OLI score questionnaire.

Domain score 1. Emotional impact

When you thought about your ostomy device and the risk of leakage, what emotions did you feel?

In the last 7 days, due to leakage or worry about leakage...	All of the time	Often	Sometimes	Rarely or never
1. I felt panic	0	1	2	3
2. I felt stressed out	0	1	2	3
3. I felt more afraid about leaks in the future	0	1	2	3
4. I felt worry	0	1	2	3
5. I felt frustrated	0	1	2	3
6. I felt embarrassed	0	1	2	3
7. I felt worried that I might leak	0	1	2	3
8. I couldn't sleep	0	1	2	3
9. I kept waking up at night to check my stoma	0	1	2	3
10. I kept checking my ostomy bag to see if I have leaked	0	1	2	3

Domain score 2. Usual and Social activities

When you thought about your ostomy device and the risk of leakage, how did it affect your activities?

In the last 7 days due to leakage or worry about leakage...	All of the time	Often	Sometimes	Rarely or never	Not applicable
11. I decided to stay at home	0	1	2	3	9
12. I couldn't do light activities	0	1	2	3	9
13. I changed my plans	0	1	2	3	9
14. I was unable to go out and meet family and friends	0	1	2	3	9
15. I avoided close physical contact with family and friends	0	1	2	3	9
16. I did not want to see people	0	1	2	3	9
17. I avoided people	0	1	2	3	9

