18. I tried to avoid meeting new people	0	1	2	3	9

Domain score 3. Coping and in control

When you thought about your ostomy device and the risk of leakage, how did it affect your ability to cope?

In the last 7 days, due to leakage or worry about leakage...	All of the time	Often	Sometimes	Rarely or never
19. I felt in control	0	1	2	3
20. I was able to cope	0	1	2	3
21. I felt calm	0	1	2	3
22. I saw my friends as I usually do	0	1	2	3

All three domain scores are designed to range from 0-100. Higher scores represent better levels of functioning. A domain score is estimated as a mean of the responses to each question or item within a domain. This is then divided by the arithmetic difference between the minimum score (0) and the maximum score (3) so that this number then varies between 0 and 1. This is then rescaled between 0 -100. It is important to note that some items in the questionnaire are effectively reversed scored. The need to do this is accommodated by in the scoring algorithm itself rather than in the scoring weights for each question. Scoring formulae for the three domain scores is provided here:

Emotional impact

$$Score = \left(\frac{\sum(Q1, Q2, \dots Q10)}{10} \div 3 \times 100 \right)$$

Usual & social activities

$$Score = \left(\frac{\sum(Q11, Q12, \dots Q18)}{8} \div 3 \times 100 \right)$$

Coping & in control

$$Score = 100 - \left(\frac{\sum(Q19, Q20, \dots Q22)}{4} \div 3 \times 100 \right)$$

Not applicable & Missing data

Where responses are classified as Not applicable then this should be noted in the descriptive summary of the data in any study report. In addition, though for the purposes of scoring the domains these responses should be coded as missing data.

A domain score can be estimated when at least 50% of the items within a domain have been completed. The scale score is estimated in the same way by taking the mean of the items that have been completed. If less than 50% of the items have been completed, then the domain should not be scored for that individual. If there are a high number of participants who fail to complete all the items in the survey, then this should be noted as a limitation in the study report.

References:

- (1) *Creating consensus-based guidelines with 2000 nurses*, Sara James-Reid et al., British Journal of Nursing 2019: <https://www.magonlinelibrary.com/doi/full/10.12968/bjon.2019.28.22.S18>

15. Appendix D – The Leakage Questionnaire

2. Antal läckage och dess storlek

[figure not shown]

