Hur många läckage har du haft de senaste 7 dagarna? _____
(se definitionen av läckage nedan)

Vad menar vi med läckage?

[figure not shown]
När du ska bedömma hur många gånger du har haft läckage under de senaste 7 dagarna, vill vi be dig att titta på exemplen nedan. Alla exemplen nedan beskriver läckage. Allt från det lilla läckaget intill stomin; när huden kommit i kontakt med avföring eller urin, till stora läckage där det har läckt ut på kläderna.

Om du under de senaste 7 dagarna kan komma ihåg hur mycket läckage du har haft vid varje läckagetillfälle ber vi dig att även fylla i antal läckage nedan under varje exempel:

[figure not shown]
Läckage - avföring

[figure not shown]
Antal _____

Antal _____

[figure not shown]

Antal _____

Antal _____

Läckage - urin

Antal _____

Antal _____

Antal _____

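### No minimum time since discharge is set for NPDs, so the 7-day baseline recall of those seen in their first week home covers hospital days, and sometimes pre-stoma days, that the follow-up recall normally does not

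*Combined protocol and SAP*

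**What the plan says.** Section 5.2 admits NPDs on "Stoma debut for < 3 months", an upper limit with no lower one. Section 5.1 asks veterans for "Stoma debut for ≥ 3 months". The background text before section 2 describes the subgroup as "newly stoma patients (i.e. newly patient discharged (NPD"), which implies that discharge has taken place but gives no number of days since.

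Section 4 states: "The NPD subgroup will follow the same protocol as the veterans". At the clinic visit this means completing the OLI score together with "recalling the number of leakage incidences the last 7 days", and doing both again after 4-5 weeks. The recall period is fixed in the instruments. The OLI stems in Appendix C begin "In the last 7 days, due to leakage or worry about leakage", and the leakage questionnaire in Appendix D asks "Hur många läckage har du haft de senaste 7 dagarna".

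Section 7 analyses the leakage count per 7 days and the three OLI domain scores by paired t-test, and section 9 makes each subject their own control. Sections 4 and 7 treat the NPD data as exploratory and keep them apart from the veteran data. The reason they give is change in the peristomal body profile; the recall window is not mentioned.

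**The concern.** A paired pre-post comparison of a 7-day count assumes that both windows cover the same kind of time. The 3-month minimum secures life with a stoma throughout the veterans' baseline window. No such rule protects the NPD window, although this is the group most likely to be seen soon after discharge.

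Two things can enter the NPD baseline window and be absent at follow-up:

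- **Hospital days**, for anyone discharged less than 7 days before the visit.
- **Pre-stoma days**, when surgery itself was less than 7 days before the visit. Leakage cannot occur on those days, so the baseline count is cut short.

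For these patients the change in leakage and OLI mixes product change with a difference in what the two windows cover. No rule in the documents adjusts the count for days with a stoma or sets such patients aside.

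**Working it through.** The plan gives no NPD sample size, power or expected change, so there is no figure of its own to reproduce. The check is arithmetic on the recall window.

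**Inputs.** The window is 7 days (section 4, Appendices C and D). Stoma age is under 3 months, taken as 90 days (section 5.2). Length of stay L, days since discharge k, the leak rate and the timing of enrolment are not in the documents and are assumed below.

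**1. Composition of the baseline window.** Home days = min(k, 7). Hospital days = min(max(7 − k, 0), L). Pre-stoma days = the remainder.

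| L | k | Home | Hospital | Pre-stoma |
|---|---|---|---|---|
| 3 | 1 | 1 | 3 | 3 |
| 5 | 1 | 1 | 5 | 1 |
| 7 | 3 | 3 | 4 | 0 |
| 10 | 5 | 5 | 2 | 0 |
| any of these | 7 | 7 | 0 | 0 |

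Any k below 7 leaves hospital days in the window. Pre-stoma days need L + k < 7.

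**2. Effect of pre-stoma days on one patient's count.** With d stoma-days at baseline, 7 at follow-up and a constant rate r, the ratio is 7r/(dr) = 7/d, whatever r is. At an assumed 0.5 leaks/day the follow-up count is 7 × 0.5 = 3.5.

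| d | Baseline count | Ratio 7/d |
|---|---|---|
| 2 | 1.0 | 3.50 |
| 4 | 2.0 | 1.75 |
| 5 | 2.5 | 1.40 |
| 6 | 3.0 | 1.17 |
| 7 or more | 3.5 | 1.00 |

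**3. Effect of hospital days.** No direction can be derived. Items 11-18 offer a 'Not applicable' answer, which Appendix C codes as missing. A domain is scored only if at least 50% of its items are completed, so the activities domain may rest on different items before and after, or go unscored. Item 22, "I saw my friends as I usually do", is the clearest item that depends on setting and has no such option. It is one of four items in its domain, each scored 0-3, so one response category is worth 100/(4 × 3) = 8.3 points and its full range is 25 points of the 0-100 score. That is a bound for one patient, not an expected shift.

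**4. Share of NPDs affected.** If enrolment is uniform from discharge to day 90 after surgery:

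- Any affected window, 7/(90 − L): L = 3 gives 7/87 = 8.0%; L = 10 gives 7/80 = 8.75%.
- Pre-stoma days, max(7 − L, 0)/(90 − L): L = 3 gives 4/87 = 4.6%; L = 5 gives 2/85 = 2.4%; L = 7 or more gives 0.

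If enrolment is instead uniform over the first 30 days after discharge, the first share is 7/30 = 23%, and the second for L = 3 is 4/30 = 13%.

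**5. Effect of truncation on the group mean count.** For L = 3, the truncated patients lack 2 days on average (4 − k, with k uniform on 0 to 4). At 0.5 leaks/day, enrolment to day 90 gives 0.046 × 2 × 0.5 = 0.046 leaks, or 1.3% of 3.5. Enrolment over 30 days gives 0.133 × 2 × 0.5 = 0.13 leaks, or 3.8%.

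**The case against.** The case for leaving the text alone has real weight.

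- **Very early enrolment is unlikely.** The group is by name discharged, section 4 describes patients with ongoing product issues who attend a clinic, and section 5.3 excludes those who need a caretaker to change the product or lack the resources to take part. This makes pre-stoma days uncommon. A reader might infer from section 5.2 alone that NPDs can be enrolled at any point after stoma formation, including on the ward; the group's own definition does not support that. Hospital days remain possible, however, because they need only a discharge within the past week. Section 5.2 also omits the re-evaluation criterion that section 5.1 sets for veterans.
- **The OLI is not tied to being at home.** This stands. A reader might infer that the items without a 'Not applicable' option must be answered as if at home, or that a hospital stay necessarily depresses the activity and coping scores. No item sets that condition, the stems tie answers to leakage or worry about it, and most emotional and coping items can be answered on a ward.
- **The data are already set apart.** They come from one site and are exploratory, unpooled and not compared with veterans. This limits the consequence, but analysing a group separately does not repair a comparison within its patients.
- **Aligned windows still leave recovery after surgery in the comparison.** This is true of any uncontrolled pre-post design, and the fix does not claim otherwise.

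**Conclusion.** The point holds, at low severity. Section 5.2 allows a baseline window that differs in kind from the follow-up window for NPDs seen within 7 days of discharge, and nothing in the documents corrects for it. The leakage bias from pre-stoma days has a known direction and a per-patient size of 7/d. The bias from hospital days has no fixed direction.

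The per-patient ratios should not be read as effects on the NPD result. Under the assumptions above, truncation moves the group mean count by about 1% to 4%, and the share with any affected window runs from about 8-9% to 23%. Both depend on assumed enrolment timing, and the truncation figure also on an assumed 3-day stay; the documents give neither. Nor do they support the inference that the NPD pre-post results as a whole cannot address the secondary objectives, since only a subset of those patients is touched. The primary usability outcome and the veteran analyses are unaffected.

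**What to change.** Add to section 5.2 that the NPD baseline questionnaire is completed at least 7 full days after discharge with the stoma. At k ≥ 7 the window contains no hospital or pre-stoma days from the stoma admission.

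If enrolment has started, record the dates of surgery and discharge; the available text does not show whether they are already collected. Limit the NPD paired OLI and leakage analyses to patients with a full 7 days at home before baseline, or report those analyses with and without the others. Keep all NPDs in the usability evaluation.

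The cost is one line in section 5.2, or two dates and one sentence on the analysis set at a single site. The downside is a slightly smaller or later NPD pre-post set, because patients in their first week home no longer contribute to it. The change aligns the recall windows only; other changes after surgery remain in the comparison and should be stated as a limitation.

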5.3. Exclusion criteria for veterans and NPDs

The subject will not be eligible for enrollment if the subject:

- Requires a caretaker to change ostomy product(s) on the user
- Is pregnant (mainly due to substantial change of body profile during intervention)
- Is lactating (mainly due to potential weight loss and substantial change of body profile during the intervention)
- Does not have the resources personally, mentally, or physically to participate in the intervention (judged by the ostomy nurse)
- Changes his/her ostomy products (bag or plate) during the intervention period (withdraw of data)

6. Number of patients with rationale for choice

A minimum of 160 subjects will be enrolled in the study. At least 40 individuals with a stoma will be enrolled from each Nordic country (i.e. Denmark, Sweden, Norway and Finland). The subjects will be recruited from at least 3 clinics in each country and each clinic will recruit at least 5 participants to the study. The total number of participants is based on what seems feasible to enroll. As the primary endpoint will be presented using descriptive methods there is no requirements on the sample size.

The OLI score results are not the primary outcome of the study and the >160 numbers of subjects are sufficient.

7. Statistical considerations

Data from the Nurse Evaluation Form will be presented using descriptive methods.

The OLI score will be presented using both descriptive methods (i.e. sub-questions) and quantitative methods (i.e. the 3 domain scores: 'emotional impact', 'usual and social activities' and 'coping and in control').

Change of the domain scores 'emotional impact', 'usual and social activities' and 'coping and in control' and number of leakages pre-and post-transition of ostomy products will be analyzed by using paired t-test. All three domain scores are designed to range from 0-100. Higher scores represent better levels of functioning. The domain scores will be calculated as mean of the responses to each question or item within a domain (the method to estimate the domain scores is described in Appendix C).

The number of leakage episodes/7 days) will be analysed by quantitative methods (paired t-test).

The exploratory NPD data from the clinical site Meilahden tornisairaala, Finland will not be pooled with the veteran data as the two groups can be potentially very different in the change of peristomal body profiles during the study period. This makes the two groups less comparable and the NPD data will therefore be analysed separately.

There will be no comparison to other types of products or body assessment tools. In case subjects change to other ostomy products during the intervention period the data of the given subject will not be included in the final data of the study.

8. Primary and secondary outcomes

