8.2. Secondary outcomes

- Rating of the user's leakage associated QoL the last 7 days (i.e. 4-point scale sub-questions) before and after ostomy product change
- Change in domain scoring of fear of leakage and the impact on QoL pre- and post-transition of ostomy product(s):
 - emotional impact
 - usual and social activities
 - coping and in control
- Number of self-reported retrospective incidences of leakage the last 7 days on prior to and after transition to more appropriate ostomy product(s)
- Analysis of connection between body profile, product solution and incidence of leakage

9. Comparison or control group

There will be no comparison to other types of products, body assessment tools or control groups.

Each subject will act as their own control when analysing the difference in the OLI score and number of leakage incidences pre-and post-transition of ostomy product(s).

10. Study follow-up schedule

No follow-up visits or contact with the users are included in the study

11. References

1. Ostomy Life Study 2019, Global Report, Data-on-file, PM-10499

12. Appendix A - Body Assessment Tool

Datum _____

Patient 3000X

Kroppsprofil

[figure not shown]
Utvärdering av den peristomala kroppsformen för att säkerställa det bästa produktvalet

1	Formen på området runt stomtin.	Platt	Området är mer eller mindre i nivå med buken, även om själva huden kan vara glömm.
		Inbuktad	Området sjunker ner i buken och bildar en grop.
		Utbuktad	Området reser sig från buken och bildar en kopp.

2	Den valda ytan kanske inte täcker hela området runt stomin	Helt	Formen täcker hela området runt stomin.
		Delvis	Formen täcker delar av området runt stomin.

3	Är magen mjuk eller fast?	Mjuk	Ytan ger vila för tryck (som motsvarar tryck på en vattenmodell).
		Fast	Ytan motstyrt tryck (som motsvarar tryck under huden).

[figure not shown]
4	Är det ytliga eller djupa veck?	Ytliga	Huden omkring stomin har linjer, dr färd eller rynkig.
		Djupa	Huden omkring stomin har djupa veck av samt rynkor.

5	Stomins placering	Över navelhöjd	Stomin är placerad över navelhöjd.

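### Removing subjects who change product after enrolment leaves the secondary pre-post tests (OLI domains, leakage count) open to selection bias

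*Combined protocol and SAP*

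**What the plan says.** The removal rule appears twice. Section 5.3, which sets exclusion criteria for both veterans and newly discharged patients (NPDs), excludes a subject who "Changes his/her ostomy products (bag or plate) during the intervention period (withdraw of data". Section 7 covers subjects who "change to other ostomy products during the intervention period the data of the given subject will not be included in the final data".

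Section 4 points the other way: "Patients will be encouraged to send in the second questionnaire even if they have discontinued using the recommended ostomy products". One stated purpose is to learn why they stopped.

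The results affected are the secondary ones. Section 7 assigns paired t-tests to the three OLI domain scores and to the number of leakages in 7 days, before and after the product change. Section 9 states: "Each subject will act as their own control when analysing the difference in the OLI score and number of leakage incidences". The first secondary objective (Section 3.2) reads: "To explore if the use of Body Assessment Tool and related change of ostomy product(s) have an impact on the leakage associated QoL".

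The plan contains no analysis of all enrolled subjects and no sensitivity analysis. It does not label the retained set as on-product, gives no expected rate of product change, and does not commit to reporting how many subjects were removed or why.

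**The concern.** Under Section 4 every subject leaves the clinic visit with new products, so the rule must mean a further change after that. Such a change cannot be screened for at entry. It is a post-baseline event used to decide whose data count.

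The event is plausibly tied to the outcome. The veterans' inclusion criterion (Section 5.1) is "Individual who require a re-evaluation of ostomy product(s) in a stoma care clinic due to issues with leakage", and someone who came in for leakage may well abandon the selected product because it leaks. Those subjects would then be missing from the tests of whether leakage and leakage-related quality of life improved. With no control group, nothing in the design offsets the selection.

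At stake is what the secondary results mean. A reader would take the mean change as describing people whose product was selected with the tool. It would describe only those for whom the selection lasted. The rule reaches all of a subject's data, so it also covers the descriptive OLI items and the separate NPD analysis.

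**Working it through.** **Is there a figure in the plan to reproduce?** Only the sample size: 4 countries × 40 = 160, which agrees with the stated minimum in Section 6. That number rests on feasibility. No effect size, SD, power or dropout rate is given, and the concern does not depend on it.

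**Passages side by side.** Section 4 asks subjects who stop the recommended product for the second questionnaire. Sections 5.3 and 7 discard it if they moved to another product. The definitions also differ: Section 5.3 names bag or plate, while Section 7 speaks of other ostomy products generally. Appendix A records accessories separately from plate and bag, so a subject who changes only an accessory could be kept under one wording and removed under the other.

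**Size of the distortion (illustration).** Let p be the share of analysable subjects who change product and f the changers' mean gain divided by the keepers' mean gain. Neither is in the documents; both are assumed.

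- Mean over everyone = keepers' mean × m, where m = (1 − p) + p·f
- Relative overstatement when only keepers are analysed = 1/m − 1

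At p = 0.15, with assumed keepers' improvements of 15 OLI points and 2.0 fewer leaks per 7 days:

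| f | m | OLI reported | OLI, everyone | Leaks reported | Leaks, everyone | Overstatement |
|---|---|---|---|---|---|---|
| 0 | 0.850 | 15.0 | 12.75 | 2.0 | 1.70 | 17.6% |
| 0.5 | 0.925 | 15.0 | 13.9 | 2.0 | 1.85 | 8.1% |
| 1 | 1.000 | 15.0 | 15.0 | 2.0 | 2.00 | 0% |
| 1.5 | 1.075 | 15.0 | 16.1 | 2.0 | 2.15 | −7.0% |

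Across other values of p:

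| p | f = 0 | f = 0.5 | f = 1 | f = 1.5 |
|---|---|---|---|---|
| 0.05 | 5.3% | 2.6% | 0% | −2.4% |
| 0.30 | 42.9% | 17.6% | 0% | −13.0% |

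These ratios do not depend on sample size or on a significance level.

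**Effect on the test (second illustration, different model).** Suppose the true mean change is 0, and the propensity to change product has correlation ρ with poor response. Under a normal selection model the bias, in SDs of the change, is ρ·φ(z₁₋ₚ)/(1 − p). At p = 0.10 and ρ = 0.5 this is 0.5 × 0.1755/0.90 = 0.097. Simulated paired t-tests (20,000 per setting, 160 subjects before removal, assumed two-sided 0.05) gave these rejection rates:

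| Removed | ρ = 0 | ρ = 0.3 | ρ = 0.5 | ρ = 0.8 |
|---|---|---|---|---|
| 5% | 0.05 | 0.07 | 0.10 | 0.20 |
| 10% | 0.05 | 0.11 | 0.22 | 0.54 |
| 20% | 0.05 | 0.22 | 0.55 | 0.96 |

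With all subjects kept, the rate stayed between 0.048 and 0.052. That last figure assumes changers' values equal what they would have been without the change. At ρ = 0 the only cost is lost subjects, for example 128 of 160 left at 20% removed.

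**The case against.** **Direction.** The second questionnaire covers only the last 7 days at week 4-5. Someone who left a leaking product would usually be answering about its replacement, which may have solved the problem. This stands: overstatement is an inference, and the f = 1.5 column shows the sign can reverse.

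**Choice of question.** Subjects are told to use the new products for 4-5 weeks, and the outcomes are framed around the product change. An on-product reading is legitimate for the second secondary objective and for the item in Section 8.2, "Analysis of connection between body profile, product solution and incidence of leakage". One can argue it also fits the first objective, and that keeping changers credits the tool with benefit from a product not chosen at that visit. The on-product analysis does deserve a place. But the first objective concerns use of the tool and the change that follows, and a selection that did not last is part of that answer. Even for an on-product question about everyone given a selected product, keeping only those who stayed on it is selective.

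**The remedy also conditions on a post-baseline event**, namely return of the second questionnaire. True, but a paired test cannot avoid it and it adds no selection beyond the plan's own. It does mean the illustrated means describe all enrolled subjects only if changers and keepers return the form equally often.

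**Weight.** The rule is pre-specified and open, the first objective is exploratory, NPDs have no leakage entry requirement, and every magnitude above is assumed. The 43% extreme needs 30% to change within 4-5 weeks with no gain in any of them. These points limit the severity; they do not supply the missing analysis.

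**Conclusion.** The concern holds. As written, the plan conditions its uncontrolled paired t-tests on an event after enrolment that is plausibly related to leakage, and it provides no analysis that retains the subjects affected. What is established is the exposure to bias. Its direction and size are not: there is none if changers gain as much as keepers. Under the assumed range of 5-30% changing product, the reported improvement would be overstated by 5-43% if changers gain nothing and by 3-18% if they gain half as much, and understated by 2-13% if they gain 1.5 times as much. The case for a link with leakage is stronger for veterans than for NPDs. The primary outcome, nurse-rated usability, is descriptive and not directly affected. The point should be fixed but does not undermine the study's main purpose.

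**What to change.** Move the last bullet of Section 5.3 out of the eligibility criteria, and replace the removal sentence in Section 7 with wording such as:

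> The main analysis of the OLI domain scores and leakage count includes every enrolled subject with a baseline and a returned second questionnaire, whatever ostomy product is in use at that time, separately for veterans and NPDs. An analysis restricted to subjects without a product change is supportive and labelled as on-product. The Section 8.2 analysis relating body profile and product to leakage uses subjects still on the recorded product, and the number excluded is stated. The numbers of product changes and of non-returners, and the reasons for change where given, are reported.

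Use one definition of product change in Sections 5.3 and 7, and reconcile both with Section 4. Confirm that the second questionnaire records whether the product was changed and why. The visible text of Appendices C and D shows no such item, but figures are missing, so its absence is not established; add one item if needed.

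The cost is wording, a second run of the same paired tests, and possibly one questionnaire item. Follow-up is already requested from these subjects, and nothing changes in how they are managed. The downsides are that the estimated improvement may be smaller, and that some week 4-5 answers will reflect a product other than the one selected. Non-return is reported but not cured.
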